These recordings will be assessed by means of an objective checklist (rubric), which assesses the errors and learning on which the educational solutions have an impact. This task will be carried out by members of the research team.

Chronological development of the project

Screening visit:

Caregivers will be informed about the study, what their commitment is, what is needed from them and the requirements. Those who are interested and meet the inclusion and exclusion criteria (described in the section Inclusion/exclusion criteria and recruitment), will be asked to sign the consent form.

Subsequently, the centers will randomly assign participants to one of the study arms and construct the registration code for each caregiver, following the guidelines in the recruitment section (the caregiver's date of birth is required).

Start-up visit (Pre-intervention):

At this point, the carers will go to the medical centre to which they belong, where they will be recorded carrying out their simulated carer's work. The recording will be made using a device consisting of neutral glasses or a headband with a small camera to record comfortably. At the beginning of the recording, the caregiver's identification code must be shown. In the same session, at the end of the recording, the centres will explain to the participants that they must fill in a questionnaire with their data, the Pre-intervention Carer's Notebook, which can be accessed from a QR code/link that will be given to them at that moment.

Subsequently, the videos of the start-up sessions of each participant will be recorded and assessed by the research team with the help of staff from the centres following the rubric provided.

Intervention:

- *Intervention application (different sessions according to arm, arms 2 to 6 only).*

At this point, the corresponding intervention will be carried out for each participant. Depending on the arm to which he/she has been assigned, the procedure and duration of the intervention sessions will be different. The information for each intervention is explained in the following sections. It will follow the following scheme:

- *Arm 1 (Control group):* no specific intervention different from the natural one is performed so it will not be necessary to convene the participants of this group for this session.

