- *Arms with intervention at home (Arm 2 - Intervention with written materials and videos, Arm 4 - Intervention with 360° materials and Arm 6 - Intervention with augmented reality):* the intervention is carried out by the caregiver alone at home, so it is useful to hold a training session at the centre to explain to the caregiver the task to be carried out at home.
- *Arms with intervention at the centre (Arm 3 - psychoeducational intervention, Arm 5 - intervention with virtual reality):* the stipulated sessions of each arm will be carried out in the rooms provided in the centres.

Post-intervention visit

Once each arm's own intervention has been received, participants will be called to participate in a new recording of the care work in the medical centre. As in the pre-intervention, at the beginning of the recording, the caregiver's identification code must be shown. At the end, a new link and QR with the Post-intervention Caregiver's Notebook will be shared with them so that they can fill it in online through the link. This flow will be for all arms except for the control arm (Arm 1), where no recording will be carried out and no post-intervention caregiver's notebook will be completed.

Again, the videos resulting from the recordings of this session should be analysed following the available rubric.

Follow-up visit (+6 months)

After 6 months (follow-up phase), participants will be recorded making two attempts at the care they were trained in. As in the previous recordings, at the beginning of the recording, the caregiver's identification code must be shown. At the end, they will be given a new QR and link to the Caregiver's Notebook Follow-up.

Gold Standard (professional group)

In addition to the participants in the control and experimental groups, the study will also include a group of 10 healthcare professionals, who will act as the Gold Standard group. This group will be recorded performing all the care situations to be trained to have a standard measure with which to compare the performance of the caregivers, once they have received the training.

Data analysis

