Time of use will be recorded and correlation analyses will be performed to determine the size and direction of the effect on the outcomes. The difference between the measures considered above rated will be considered before and after (PRE and POST intervention (time 0) and FOLLOW UP (+6 months)) the experimental intervention sessions as outcome variables. The distribution of the data will be tested using the Kolmogorov-Smirnov test, the measures will be compared with an ANOVA test for normally distributed continuous variables, and the Kruskal-Wallis test if the distribution is not normal. Given the number of time-ordered and repeated variables per subject, they will be explored using a linear mixed effects model (LMM). Data will be stratified taking into account gender, age, recipient profile and time of use. P values <0.05 are considered to indicate statistically significant differences. Statistical analyses will be performed on R and SPSS. If the intervention is successful, the control group will be invited to receive the treatment of the experimental group on the same terms. The results of this project will be prepared for dissemination according to the contents of the "Standards for reporting qualitative research" (SRQR) guidelines for qualitative studies, the Consort checklist for randomized trials, and the CHEERS checklist for economic outcome evaluations.

Discussion sobre utilidad o lo que hacen otros estudios

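### Time of use arises after randomisation but is listed as a stratification factor beside baseline variables; arm contrasts stratified by it lose the protection of randomisation

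*Combined protocol and SAP*

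**What the plan says.** The Data analysis section has two sentences on time of use. It opens with: "Time of use will be recorded and correlation analyses will be performed to determine the size and direction of the effect on the outcomes". Later, after naming ANOVA or Kruskal-Wallis for the comparison of measures and a linear mixed model for the repeated data, it adds: "Data will be stratified taking into account gender, age, recipient profile and time of use". The four factors have equal rank. Time of use is not defined, is not confined to exploratory or within-arm analysis, and has no stated value for the control arm.

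The section on the chronological development of the project gives the order of events:

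- **Screening visit**, after consent: "Subsequently, the centers will randomly assign participants to one of the study arms". This precedes the pre-intervention visit and all training.
- **Intervention**, sessions: "different sessions according to arm, arms 2 to 6 only". Also, depending on the arm, "the procedure and duration of the intervention sessions will be different".
- **Intervention**, arms 2, 4 and 6: "the intervention is carried out by the caregiver alone at home". For arms 3 and 5: "the stipulated sessions of each arm will be carried out in the rooms provided in the centres".
- **Post-intervention visit**: the control arm has neither a recording nor a notebook, so it contributes pre-intervention and 6-month data only.

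**The concern.** Randomisation makes the arms comparable in everything fixed before assignment. Stratifying by such a variable keeps that comparability; stratifying by something the assignment itself changes does not. If one format gets carers to use it more, its low-use stratum holds unusually unmotivated carers, and its high-use stratum includes carers who would have used another format only moderately. Within each stratum the arms then contain different kinds of carer. The more engaging arm can look worse in every stratum without being worse overall.

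The Abstract's aim is to find the most effective educational solution, which is a between-arm comparison. Two further consequences follow. Contrasts with control cannot be formed in strata where control has no members. And a correlation between use and outcome, which the plan says will determine an effect, is a non-randomised association that can be positive even if use does nothing.

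**Working it through.** **1. Timing.** The plan has no figure on this point to reproduce, so the passages are set side by side.

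| Factor | Fixed before assignment? | Can the arm change it? |
|---|---|---|
| Gender, age, recipient profile | Yes | No |
| Time of use (read as use of the assigned material) | No | Yes: session procedure and duration differ by arm |

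In arms 2, 4 and 6 use also depends on the carer, who works alone at home. Time of use therefore reflects both assignment and, at least there, carer behaviour.

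**2. Control.** Sessions are for arms 2 to 6, so by inference control's time of use is zero or missing. No allocation ratio is stated. With equal probability, the expected number of controls is 420 / 6 = 70, and the Binomial(420, 1/6) 2.5th to 97.5th percentile range is 55 to 85.

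- *Coded missing:* no control enters any stratum.
- *Coded zero, tertiles over all 420, positive use elsewhere:* the lowest tertile has 420 / 3 = 140 people, about 70 controls and 140 - 70 = 70 low users from other arms. The other two tertiles have no controls.

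Control's only outcome contrast is at 6 months. It is absent from every positive-use stratum and, in a lowest stratum that mixes zero and low use, compares controls with a selected set of low users.

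**3. Illustration for two active arms.** All inputs are assumptions, since the documents give none:

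- motivation U ~ N(0,1);
- use T = r·U + √(1 − r²)·e + s·Arm, with r = 0.3, 0.5 or 0.7 and s = 0, 0.5 or 1.0 SD;
- outcome = change score (the plan's outcome), with no effect of arm or use;
- (A) motivation correlates g = 0.3 or 0.5 with improvement; (B) motivation affects pre and post equally, so it cancels from the change.

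The stratified difference is the size-weighted mean of within-stratum arm differences. Results for (A), in SD of the change score, with at least 1,000,000 simulated participants per scenario:

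| r | g | s | Unstratified | Median split | Tertiles |
|---|---|---|---|---|---|
| 0.3 | 0.3 | 0.5 | 0.00 | -0.03 | -0.04 |
| 0.7 | 0.3 | 0.5 | 0.00 | -0.07 | -0.08 |
| 0.5 | 0.5 | 1.0 | 0.00 | -0.16 | -0.20 |
| 0.7 | 0.5 | 1.0 | 0.00 | -0.22 | -0.28 |
| any | any | 0 | 0.00 | 0.00 | 0.00 |

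Under (B) the stratified difference is 0.00 throughout.

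**4. False-positive rate at trial size.** A separate simulation used two arms of 70, no true effect, r = g = 0.5, a two-sided 0.05 test (sidedness assumed) and 4,000 replicates. The unstratified error rate was about 0.05. Stratified by tertiles of use, it was 0.09 for s = 0.5 (bias -0.10 SD) and 0.19 for s = 1.0 (bias -0.20 SD). With s = 0 it stayed at about 0.05.

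**5. Correlation.** Under (A), with use having no effect, the within-arm correlation of use with outcome is r·g: from 0.3 × 0.3 = 0.09 to 0.7 × 0.5 = 0.35. It does not depend on s, so it persists even when use is equal across arms. Under (B) it is 0.00.

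**The case against.** The strongest reply is that the plan never says the arm comparison is the stratified analysis. It states that "the measures will be compared with an ANOVA test for normally distributed continuous variables", then names the mixed model, in both cases without a stratifier. The later sentence could mean subgroup description or a dose-response analysis within arms. This stands as a limit on reach: an unstratified ANOVA, Kruskal-Wallis or mixed-model comparison is not harmed. It does not remove the problem. The sentence follows directly on those analyses, no primary analysis is named, and results by arm within strata of use would comply with the plan as written.

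Second, control's zero or missing use is an inference. Arm 1 does receive ordinary information and answers to questions, and time of use is undefined. That is fair. If control is coded zero and the lowest stratum also takes in low users, some contrast with control survives there, though confounded. The 6-month control contrast is lost only within positive-use strata, not from the trial.

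Third, the magnitudes are assumed. The documents support session differences by arm but say nothing of a common cause of use and improvement. The figures show that bias can arise, not that it will.

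Fourth, a correlation coefficient does report size and direction, and the word effect is often used loosely. That sentence is the smaller point, but as written it invites a causal reading.

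**Conclusion.** The concern holds and should be fixed. Listing a post-assignment variable as a stratifier without restriction is a poor analysis rule, not merely a missing detail. That conclusion rests on the plan's own order of events and on reading time of use as use of the assigned material; it does not depend on the simulation.

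The size cannot be known from the documents. Under the stated assumptions the false arm difference is -0.03 to -0.22 SD (median split) or -0.04 to -0.28 SD (tertiles). Bias between active arms needs use to differ by arm and, with no true effect as assumed here, to share a cause with improvement. The unstratified comparison remains valid in this respect, so this is a correctable fault in one part of the analysis and does not undermine the trial.

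**What to change.** Replace the stratification sentence in Data analysis with:

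> Arm comparisons will be analysed as randomised and stratified or adjusted only for baseline variables (gender, age, recipient profile). Time of use will be defined and reported descriptively by arm; its within-arm correlation with outcomes (arms 2 to 6) is an exploratory association.

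In the opening sentence of the section, delete the clause saying that the correlation will determine an effect on outcomes. The definition of time of use should say what is counted, how it is measured for home and centre arms, and how Arm 1 is coded. Comparing carers as randomised follows from the same principle, since grouping them by what they actually received would also condition on a post-assignment event.

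The cost is wording only: design, data collection and sample size do not change. The one loss is that time of use can no longer break down the arm contrasts. The dose-response question survives as a labelled within-arm analysis.

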The project seeks to put people at the center of interventions while respecting their digital rights. The comparison between 360V, VR, RA, web-based information, written information and standard procedure, to determine which is the best way to train home caregivers in order to increase their technical competences and soft skills, including self-confidence, is the outcome this project would analyze. This study aims to explore the

experience and needs of caregivers (skilled and unskilled) of dependent and chronically ill patients and then to design and test the effectiveness of several interventions aimed at promoting safer medication use in the home.

Methods

Intervention design

This is a prospective, parallel, fully randomized (with simple random assignment of participants to one of six arms) experimental study to compare (inter-group and intra-subject PRE and POST measures) educational interventions aimed at training caregivers using typical scenarios during their work at home in order to reduce medication and caring errors and improve caregivers' motivations and self-efficacy.

Present protocol underwent the revision and approval of an Ethics Committee Board, obtaining the approval in December 2021 and January 2023 (CODES 21/063; 22/079 and 22/080). ClinicalTrial xxxxxxxx

Recruitment

Recruitment will be carried out in the collaborating centers through the programmes for complex chronic patients, schools for carers, and associations and foundations for carers and/or diseases causing dependency situations using the "snowball" technique.

Participants (caregivers) will be recruited during a regular consultation where they go to accompany the person they care for to the consultation, or in a clinical consultation of their own where they can comment that they are caring for a person at home. Recruitment will be carried out through systematic sampling according to the list of people seen in the consultation, using $k=3$. The collaborator will systematically select 1 out of every 3 patients cited in the consultation list. If the person refuses to be included in the study, the next person on the list will be invited and then $k=3$ will be applied.

Additionally, in the recruitment of caregivers, two aspects must be considered:

- Qualification of the caregivers

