- *Arm 2-Experimental group 2:* Intervention with written materials and demonstration videos specifically designed for this study. **This arm will evaluate the effect of a traditional, more passive form of learning, with little degree of interaction with the content.**
- *Arm 3-Experimental group 3:* Psychoeducational intervention specifically designed for this study. **With this specific intervention, participants will learn by sharing information with the session facilitator and other participants, which will facilitate a more active form of learning, with a higher degree of interaction than the previous arm.**
- *Arm 4-Experimental group 4:* Intervention using immersion 360 degrees specifically designed for this study. **Participants enrolled in this arm, by completing it, is assumed that will experience a form of learning more participatory and immersive than conventional videos, as they can interact with the content by changing the camera angle.**
- *Arm 5-Experimental group 5:* Virtual Reality intervention specifically designed for this study. **Using VR to learn procedures will encourage caregivers to learn in a fully immersive and participatory environment where they will have to interact with the virtual content, enhancing their learning experience.**
- *Arm 6-Experimental group 6:* Augmented Reality Intervention specifically designed for this study. **This intervention will increase participants' skills through active learning as they interact with real-world care situations while receiving simultaneous support from AR devices.**

In each of the experimental groups, key patient care situations will be developed and the educational solutions for each of the arms will be adapted.

The process of this phase of the study is summarized in the following **figure**.

The evaluation of the effectiveness of each of the arms will be measured, among other ways, by recording two attempts to execute the care situation to be trained in the intervention. This recording will be made at three different times: at the baseline visit (pre-intervention), after the intervention (post-intervention) and 6 months after the end of the intervention (follow-up). The control group is an exception, as there is no specific intervention and therefore the post-intervention recording is omitted. Thus, in the case of the control group, only the pre-intervention and 6 months after the intervention will be recorded.

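### P<0.05 is applied to every measure and time window with no primary outcome, primary time point or multiplicity rule, so the false-positive risk exceeds 5% by an amount the documents do not fix

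*Combined protocol and SAP*

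**What the plan says.** The Data analysis section is the whole statistical plan. On outcomes it says: "The difference between the measures considered above rated will be considered before and after", and it then lists pre-intervention, post-intervention and 6-month follow-up as the times. On tests it says: "the measures will be compared with an ANOVA test for normally distributed continuous variables, and the Kruskal-Wallis test if the distribution is not normal". A linear mixed model is mentioned for the repeated measures, and the data are to be stratified by four factors. The only decision rule is "P values <0.05 are considered to indicate statistically significant differences".

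No list of measures precedes that section. What can be found is:

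- Overview and aim says of the project's purpose: "increase their technical competences and soft skills, including self-confidence, is the outcome this project would analyze".
- The first Intervention design section, under Methods, says the training is given "in order to reduce medication and caring errors", and adds carers' motivation and self-efficacy.
- The later Intervention design section, under Phase 2, says: "The evaluation of the effectiveness of each of the arms will be measured, among other ways, by recording two attempts". The recordings are scored with a rubric, and they are not the only measure.
- The visit descriptions add an online Caregiver's Notebook at each recorded visit. Its contents are not given.

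None of these is called primary. The control arm has no post-intervention recording or notebook; it is measured only before the intervention and at 6 months.

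**The concern.** A 0.05 threshold gives a 5% error rate for one test. Here it governs an unstated number of tests, spread over several constructs and more than one time window, and nothing says which of them decides the trial. Two consequences follow. The chance of at least one spurious significant arm difference is above 5%. And the measure and window reported as the result can be picked after the data are seen.

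This matters because the plan draws conclusions from the result. The Abstract promises to identify the most effective educational solution, and the Data analysis section offers the training to the control group if the intervention succeeds, without defining success. The problem arises even if each measure receives only one omnibus test, so it is separate from the question of which arms are compared with which.

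**Working it through.** **The plan's own figure.** The plan states no familywise error rate, so there is none to reproduce. The total of 420 cannot be reproduced either, because no power, effect size, standard deviation or dropout is given. It serves only as an input.

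**Inputs from the documents.** Six arms; 420 participants; threshold 0.05; three measurement times, with control missing the post-intervention time; one omnibus test per measure.

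**Assumptions.** Equal arms, 420/6 = 70 (simple randomisation will not give this exactly). Correlation 0.5 between visits. Outcome correlation 0.3 to 0.8. Normal data, so ANOVA rather than Kruskal-Wallis. One, two, four or six measures. Either two windows (post minus pre, follow-up minus pre) or three (adding follow-up minus post). No true difference between any arms.

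**Step 1: independent tests.** For m independent tests, the chance of at least one P<0.05 is 1 − 0.95^m.

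- m = 2: 9.75%
- m = 4: 18.5%
- m = 6: 26.5%
- m = 8: 33.7%
- m = 12: 46.0%

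These are reference values only, since measures and windows on the same carers are correlated.

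**Step 2: simulation with correlation.** Change scores were compared by one-way ANOVA. Windows that use the post-intervention visit include arms 2 to 6 only, so F has 4 and 5 × 69 = 345 degrees of freedom. Follow-up minus pre includes all six arms, so F has 5 and 6 × 69 = 414. There were 2,000 runs per setting, with Monte Carlo standard error about 1 percentage point. The chance of at least one P<0.05 was:

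| Measures | Outcome correlation | Follow-up minus pre only | Two windows | Three windows |
|---|---|---|---|---|
| 1 | – | 4.4% | 9.4% | 13.7% |
| 2 | 0.3 | 10.6% | 18.6% | 24.6% |
| 2 | 0.8 | 8.6% | 15.6% | 20.5% |
| 4 | 0.3 | 17.6% | 31.4% | 40.2% |
| 4 | 0.8 | 11.4% | 20.6% | 27.8% |
| 6 | 0.3 | 22.5% | 39.4% | 50.2% |
| 6 | 0.8 | 15.2% | 27.6% | 35.0% |

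Separate repeat runs agree to within simulation error. Taken together, over two or three windows, the ranges are about 9–13% for one measure, 15–24% for two, 21–41% for four and 27–53% for six. Even with a single window, several measures exceed 5%.

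**Step 3: what one primary test would and would not control.** One measure, one window and one omnibus test at 0.05 has a 5% error rate (the 4.4% above is within simulation error of that). The omnibus test does not say which arm differs from control. Unadjusted follow-on tests on that one measure would give at least one false positive in about 18% of null trials for the five comparisons with control, and 36% for all 15 pairs.

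**The case against.** The strongest reply is that the number of tests is not known. The documents name constructs in their statements of aim, not a list of scores. Self-confidence is named as part of soft skills, so counting both would count it twice. The only scored instrument described is the rubric, and errors and technical competence may all come from it as highly correlated scores. A separate test of follow-up minus post-intervention is also not spelled out. All of this stands. A reader might infer that the trial has a fixed false-positive chance of, say, 22–55%. The documents do not support that: such a range needs roughly two to six measures, three windows and outcome correlations of 0.3 to 0.6, none of which they state.

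A reader might also infer that the inflated rate is the chance of wrongly concluding that training beats the natural intervention. That goes too far. Windows using the post-intervention visit exclude control, so a false positive there is a difference among training arms. Even the six-arm omnibus test can reject because training arms differ from one another.

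Third, the plan proposes a mixed model. One joint arm-by-time test per outcome could reduce multiplicity across windows. But the plan says only that the repeated variables are such that "they will be explored using a linear mixed effects model (LMM", and gives neither terms nor a key test. Multiplicity across outcomes would remain.

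Finally, the stratified analyses might be expected to raise the error further. The plan does not say whether strata will be tested for significance, and this was not simulated, so no size is claimed.

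None of these points supplies a primary outcome, a primary time point or an adjustment.

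**Conclusion.** The defect holds. The plan applies 0.05 to several measures over several windows and names no primary analysis, so the chance of at least one false significant arm difference is above 5% whenever more than one measure or window is tested. That much rests on the text alone.

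The size does not. For two to six measures over two or three windows it lies at roughly 15–53%, given 70 per arm, visit correlation 0.5, outcome correlation 0.3 to 0.8 and one omnibus ANOVA per measure and window. For one measure it falls to 9–13%. These figures concern any difference among the arms tested, not specifically benefit over control, and they exclude stratified analyses and pairwise follow-on tests.

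**What to change.** Before data are examined:

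1. Name one primary outcome and time point: the rubric error score at 6 months, the only post-baseline time at which all six arms are recorded. State how the two attempts are combined into one score. Apply 0.05 to that test.
2. Make claims for individual arms against control on that outcome with a procedure that controls familywise error over the five contrasts, for example Dunnett, or Holm (smallest P compared with 0.05/5 = 0.01).
3. Treat the other measures and windows either as secondary with Holm adjustment, or as exploratory with confidence intervals and no claim of significance.
4. Label the stratified analyses exploratory.

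No new visits or data are needed, but this is more than an editorial change. Secondary and self-report outcomes lose standalone claims at 0.05. The primary question becomes performance at 6 months rather than immediate learning, which the sponsor must accept knowingly. The control arm's 6-month date also needs a defined starting point, because follow-up is timed from the end of the intervention and that arm has no intervention session.
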